# 1 ABBREVIATIONS & DEFINITIONS

## 1.1 ABBREVIATIONS

**ACURASYS** = The ARDS and Curarisation Systematic study investigators

**ARDS** = Acute Respiratory Distress Syndrome

**BiPAP** = Bilevel Positive Airway Pressure

**BMI** = Body Mass Index

**BUN** = Blood Urea Nitrogen

**CCC** = Clinical Coordinating Center

**CPAP** = Continuous Positive Airway Pressure

**DSMB** = Data Safety Monitoring Board

**ECMO** = Extracorporeal Membrane Oxygenation

**EDEN** = Early versus Delayed Enteral Nutrition trial

**FACTT** = Fluid and Catheter Treatment Trial

**FiO2** = Fraction of Inspired Oxygen

**GCS** = Glasgow Coma Scale

**GRADE** = Grading of Recommendations Assessment, Development and Evaluation

**IBW** = Ideal Body Weight

**ICU** = Intensive Care Unit

**IL-1 $\beta$**  = Interleukin 1 $\beta$

**IL-6** = Interleukin 6

**IL-8** = Interleukin 8

**IMV** = Intermittent Mechanical Ventilation

**INR** = International Normalized Ratio

**ITT** = Intent to Treat

**IVRS** = Interactive Voice Response System

**LAR**=Legally Authorized Representative

**LTAC** = Long Term Acute Care Facility

**mBW** = Measured Body Weight

**MRC** = Medical Research Council

**NHLBI** = National Heart Lung and Blood Institute

**NMBA** = Neuromuscular blocking agent

**OSCILLATE** = Oscillation for Acute Respiratory Distress Syndrome Treatment Early

**PETAL** = Prevention and Early Treatment of Acute Lung Injury

**P/F** = PaO2/FiO2 ratio

**PaCO2** = Partial pressure of arterial carbon dioxide

**PaO2** = Partial pressure of arterial oxygen

**PAP** = Pulmonary Artery Pressure

**PB** = Barometric Pressure

**PBW** = Predicted Body Weight

**PEEP** = Positive End-Expiratory Pressure

**PIN** = Personal Identification Number

**Pplat** = Plateau pressure

**PROSEVA** = Proning Severe ARDS Patients study investigators

**PTSD** = Post Traumatic Stress Disorder

**PS** = Pressure Support Ventilation

**RASS** = Richmond Agitation Sedation Scale

**S/F** = SpO2/FiO2 ratio

**SOFA** = sequential organ failure assessment

**SBP** = Systolic Blood Pressure

**SBT** = Spontaneous Breathing Trial

**SpO2** = Oxygen Saturation via pulse oximetry

**SUSAR** = Serious and Unexpected Suspected Adverse Reactions

**SAEs**= Adverse events that are serious and unexpected and have a reasonable possibility that the event was due to a study procedure

**VFD** = Ventilator-free Days

**WBC** = White Blood Cell

## 1.2 DEFINITIONS

**Adverse Event:** Any untoward medical occurrence associated with the use of a drug or a study procedure, whether or not considered drug related.

**Adverse reaction:** An adverse reaction means any adverse event caused by a drug. An adverse reaction are a subset of all suspected adverse reactions where there is a reason to conclude that the drug caused the event.

**Assisted breathing:** Any level of ventilatory support at pressures higher than the unassisted breathing thresholds. Completing 48 hours of UAB is defined as the date (calendar day) that the subject reaches exactly 48 hours of UAB. Example: if subject meets UAB at 1900 on 6/1/15 and does not return to assisted breathing, then the date of completing 48 hours of UAB would be 6/3/15.

**Controlled Ventilation:** Any mode with a backup rate that allows clinicians to either set tidal volume to a target or adjust pressures to target a tidal volume. Examples include volume assist control, pressure assist control, pressure regulated volume control.

**Extubation:** Removal of an orotracheal, nasotracheal tube, or unassisted breathing with a tracheostomy

**Home:** Level of residence or health care facility where the patient was residing prior to hospital admission.

**Intention to Treat (ITT):** All eligible and consented patients who undergo randomization will be included in the ITT cohort for the purposes of analyzing the primary and secondary study outcomes.

**Invasive Mechanical Ventilation:** Assisted ventilation delivered by a nasotracheal, orotracheal, or tracheostomy tube

**Legal Representative:** An individual, judicial, or other body authorized under applicable law to consent on behalf of a prospective patient to the patient's participation in the clinical study.

**Mortality prior to discharge home before day 90:** This primary outcome includes deaths from all causes following randomization in any health care facility prior to discharge home until study day 90. Study subjects still in a health care facility at study day 91 are considered alive for this endpoint.

**Funding:** National Institutes of Health (National Heart Lung and Blood Institute)

**Sponsor:** The Clinical Coordinating Center at Massachusetts General Hospital

**Study Day:** The day of randomization is study day zero. The next day is study day one etc.

**Study Drug:** Randomly assigned cisatracurium

**Study hospital:** Defined as the hospital where the patient was randomized and enrolled.

**Study withdrawal:** Defined as permanent withdrawal from study before completion of study activities. This does not include those subjects who have completed the protocol procedures or stopped procedures because they have reached unassisted breathing. If a patient or surrogate requests withdrawal from the study the clinician should seek explicit permission to continue data collection.

**Suspected adverse reaction:** any adverse event for which there is a reasonable possibility that the drug caused the adverse event. Reasonable possibility means there is evidence to suggest a causal relationship between the drug and the adverse event. A suspected adverse reaction implies a lesser degree of certainty about causality than adverse reaction (21 CFR 312.32(a))

**UAB (Unassisted Breathing):** Spontaneously breathing with face mask, nasal prong oxygen, room air, T-tube breathing, tracheostomy mask breathing, CPAP  $\leq$  5 without PS or IMV assistance, the use of noninvasive ventilation solely for sleep-disordered breathing, or use of a nasal high flow system.

## 2 TRIAL SUMMARY

**Title:** Reevaluation Of Systemic Early neuromuscular blockade (ROSE)

**Objective:** To assess the efficacy and safety of early neuromuscular blockade in reducing mortality and morbidity in patients with moderate-severe ARDS in comparison to a control group with no routine early neuromuscular blockade.

**Hypothesis:** Early neuromuscular blockade will improve mortality prior to discharge home before day 90, in patients with moderate-severe ARDS.

**Study Design:** Multi-center, prospective, 2-arm, unblinded, randomized clinical trial of two management strategies of neuromuscular blockade (also called skeletal muscle relaxant and muscle relaxant).

1. We will emphasize early screening and protocol initiation, and enroll a maximum of 1408 patients with a confirmed and established PaO2/FiO2 < 150.
  - ✓ We will allow determination of PaO2/FiO2 inclusion criteria from SpO2 pulse oximetry measurement.
2. Early neuromuscular blockade group
  - ✓ Patients will receive a cisatracurium besylate bolus of 15 mg, followed by a continuous infusion of 37.5 mg/hour for 48 hours.
  - ✓ We will protocolize deep sedation to Ramsay of 5-6 (RASS of -4 to -5, or Riker of 1-2) before starting, and during, the 48 hour infusion. We do not mandate sedative type or dose.
  - ✓ We will protocolize high PEEP/FiO2 titration (based on published, safe, feasible high PEEP protocols).
3. No routine early neuromuscular blockade group (control group)
  - ✓ We will recommend non-neuromuscular blockade interventions for refractory hypoxia and that neuromuscular blockade only be used for refractory elevated plateau pressure; treating clinicians can use neuromuscular blockade if thought necessary
  - ✓ We will recommend clinicians target light sedation titrated to a Ramsay 2-3 (RASS of 0 to -1, or Riker 3-4) and/or perform daily sedation interruption. Higher doses of sedation will be allowed for respiratory distress, ventilator dyssynchrony, or hypoxia. We do not mandate sedative type or dose.
  - ✓ We will protocolize high PEEP/FiO2 titration (based on published, safe, feasible high PEEP protocols).
4. Prone positioning
  - ✓ We will recommend sites wait at least 12 hours (as per PROSEVA[1]) before proning, and to avoid automatic use of neuromuscular blockade with proning.
5. Other care

- ✓ We will protocolize low tidal volume ventilation and spontaneous breathing trials in both arms.
- ✓ We will provide recommendations for conservative fluid management in both arms.

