- a) Oxygenation Index on study days 1-4,7
- b) PaO2 / FiO2 ratio on study days 1-4, 7
- c) Level of PEEP on study days 1-4, 7
- d) Plateau pressure on study day 1-4, 7
- e) Development of pneumothorax through day 7

9. Long term outcome assessments

We will assess seven measures after hospitalization:

- a) Disability: using Katz Activities of Daily Living (ADL)/Lawton Instrumental Activities of Daily Living Scale (IADL) plus two additional Nagi items
- b) Health-Related Quality of Life (including utilities): EuroQol (EQ-5D-5L)
- c) Self-rated health: 1 standard item
- d) Pain-interference: 1 standard item
- e) Post-traumatic Stress-like Symptoms: Post-Traumatic Stress Symptoms (PTSS-14)
- f) Cognitive function: Montreal Cognitive Assessment (MoCA-Blind) or, via proxy, the Alzheimer's Disease 8 (AD8)
- g) Subsequent return to work, hospital and ED use, and location of residence

These measures will be collected through telephone interviews with patients or their LARs (Appendix G).

10. Use of rescue procedures

Rescue procedures will be chosen according to the practice at the clinical site. We will record the use of the following rescue procedures (yes/no) through study day 28: prone positioning, nitric oxide, epoprostenol sodium, high frequency ventilation, and ECMO.

11. Paralysis recall, in-hospital

Paralysis recall assessment will be monitored once during hospitalization in all patients, using a modified Brice questionnaire [22, 23].

12. Supraventricular tachycardia (SVT) or new onset atrial fibrillation (the occurrence of one or more episodes during the ICU stay will be recorded)

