### 5.2.1 MINIMIZING NEUROMUSCULAR BLOCKADE

We will encourage sites to minimize neuromuscular blockade use in the control arm.

Our goal is to respect clinician autonomy and protect patient safety, while preserving separation of treatment between arms. We will encourage non-neuromuscular blockade interventions for refractory hypoxia such as recruitment maneuvers, proning without neuromuscular blockade, deeper sedation, and consider a trial of diuresis. The threat of higher use of these interventions

in the control arm is outweighed by the necessity of having a separation in neuromuscular blockade treatment between arms.

**Recommendation:** If the end-inspiratory plateau pressure remains greater than 32 cm of water for at least 10 minutes, it is recommended that the patient receive the administration of increasing doses of sedatives and decreasing tidal volume and positive end-expiratory pressure (if tolerated) before considering using open-labeled cisatracurium. If the treating physician still wants to administer a neuromuscular blocking agent, an open-label, rapid, intravenous injection of 20 mg of cisatracurium will be recommended for patients in the control or treatment arms of the study. If this rapid, intravenous injection results in a decrease of the end-inspiratory plateau pressure by less than 2 cm of water, a second injection of 20 mg of cisatracurium will be allowed. If after injection, the end-inspiratory plateau pressure does not decrease or decreases by less than 2 cm of water, cisatracurium should not be administered again during the following 24-hour period.

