### 5.3.2 PRONING

We will recommend sites wait at least 12 hours (as per PROSEVA[1]) before proning, and to avoid automatic use of neuromuscular blockade with proning.

Based on the results of our survey of PETAL investigators, we expect modest use of proning in either arm of this study. Overall, half of the investigators reported that proning was initiated in less than 40% of ARDS patients with a P/F < 150.

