## Appendix:

### Appendix A1: Outcome Variables

Variable	Category	Scale	Method
All-cause mortality prior to discharge home before day 90	Primary Outcome	Binary	Wald-test from 90 day KM estimate
ICU acquired weakness	Secondary Outcome	Binary	Monte Carlo Fisher's Exact Test
IL-6 levels (plasma)	Secondary Outcome	Continuous	T-test
Hospital mortality to day 28	Secondary Outcome	Binary	Chi-square Test
Ventilator free days to day 28	Secondary Outcome	Continuous	T-test
Organ failure free days to day 28	Secondary Outcome	Continuous	T-test
ICU-free days at day 28	Secondary Outcome	Continuous	T-test
Hospital-free days at day 28	Secondary Outcome	Continuous	T-test
Oxygenation Index on study days 1-4,7 PaO 2 / FiO 2 ratio on study days 1-4, 7 Level of PEEP on study days 1-4, 7 Plateau pressure on study day 1-4, 7 Development of pneumothorax through day 7	Physiologic measure	Continuous Continuous Continuous Continuous Binary	T-test T-test T-test T-test Fisher's Exact Test
Disability: using Katz Activities of Daily Living (ADL)/Lawton Instrumental Activities of Daily Living Scale (IADL)	Long term outcome assessments	Binary	Chi-square Test

plus two additional Nagi items			
Health-Related Quality of Life (including utilities): EuroQol (EQ-5D-5L)		Continuous	T-test
Self-rated health: 1 standard item		Continuous	T-test
Pain-interference: 1 standard item		Continuous	T-test
Post-traumatic Stress-like Symptoms: Post-Traumatic Stress Symptoms (PTSS-14)		Binary (Part B Score $\geq 45$ )	Chi-square Test
Cognitive function: Montreal Cognitive Assessment (MoCA-Blind)		Continuous Binary ( $< 26$ )	T-test Chi-square Test
Via proxy, the Alzheimer's Disease 8 (AD8)		Continuous	T-test
Subsequent return to work, hospital and ED use, and location of residence		Categorical	Fisher's Exact Test
Use of rescue procedures	Safety	Binary	Fisher's Exact Test

Paralysis recall, in-hospital	Safety	Binary	Fisher's Exact Test
Supraventricular tachycardia (SVT) or new onset atrial fibrillation	Safety	Binary	Fisher's Exact Test

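### Proning is encouraged in the control arm only but counts as rescue, so a between-arm difference in rescue use cannot be read as need for rescue or as safety of blockade

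*Protocol*

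**What the plan says.** - **Advice to controls.** Protocol section 2, Study Design item 3 (control group): "We will recommend non-neuromuscular blockade interventions for refractory hypoxia and that neuromuscular blockade only be used for refractory elevated plateau pressure". That sentence does not name proning. Section 5.2.1, within the control-group section, does. It encourages measures "such as recruitment maneuvers, proning without neuromuscular blockade, deeper sedation, and consider a trial of diuresis". Section 5.1, on the blockade arm, has no counterpart.
- **The trade-off is acknowledged.** Section 5.2.1 speaks of "The threat of higher use of these interventions" among controls, and accepts it for the sake of keeping the arms apart on blockade.
- **Both arms.** Section 5.3.2 advises on the timing of proning and against automatic blockade with it, and adds that "we expect modest use of proning in either arm of this study". Section 5.3.6 permits proning as rescue in either arm when oxygenation targets cannot be held on an FiO2 of 1.0.
- **The outcome.** Section 3.9.2 item 10: "We will record the use of the following rescue procedures (yes/no) through study day 28: prone positioning, nitric oxide", followed by epoprostenol, high frequency ventilation and ECMO. The recording rule carries no oxygenation threshold.
- **The analysis.** SAP 1.5 lists rescue use as a secondary outcome. SAP Appendix A1 has one row, "Use of rescue procedures", with category Safety, scale binary and method Fisher's exact test. SAP 2.3 sets a two-sided 0.05 level without multiplicity correction. SAP 2.9 adds an instrumental-variable estimate of the effect of treatment received for secondary end points on which assignment has a significant effect.

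**The concern.** An outcome classed as Safety and named for rescue invites the reading that the arm with more events had more patients whose oxygenation failed. Here one component is also something that clinicians in one arm, unblinded, are encouraged to do. The count can therefore differ between arms with no difference in need. It could also hide a real excess of need in the cisatracurium arm. The protocol weighs the imbalance for the conduct of the trial, but neither document says what it does to this outcome. SAP 2.9 makes the matter concrete, because a significant result would lead to an estimate attributed to the blockade received.

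**Working it through.** **1. The two rules for proning, side by side.** Section 5.3.6 ties rescue to failure to hold oxygenation targets on an FiO2 of 1.0. Section 3.9.2 item 10 counts any proning to day 28. Section 5.3.2 expects some proning in both arms and does not tie that expectation to the 5.3.6 threshold. So proning outside rescue is counted as rescue, and it is encouraged in one arm.

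**2. Sample size.** The documents give no figure for the rescue outcome. The primary calculation supplies the number per arm. With 35% and 27% mortality, two-sided alpha 0.05 and power 0.90:

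n per arm = [1.960·√(2·0.31·0.69) + 1.282·√(0.35·0.65 + 0.27·0.73)]² / 0.08² ≈ 701, or 1402 in total, against the stated 1408.

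At 704 per arm the power is 0.90, so the plan's figure reproduces. I use 704 per arm below. Equal allocation is my assumption, as no ratio is stated, and 1408 is a maximum.

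**3. How often advice alone would give p<0.05.** Assume that the drug has no effect on need for rescue, and that rescue use is p in the blockade arm and p + δ in controls, with δ due only to the advice. The table gives the share of 4,000 simulated trials per cell with two-sided Fisher p<0.05.

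| Base rate p | δ = 0 | δ = 2 points | δ = 3 points | δ = 5 points |
|---|---|---|---|---|
| 10% | 4.3% | 19.6% | 38.1% | 79.8% |
| 20% | 4.4% | 14.0% | 24.8% | 58.8% |
| 30% | 3.6% | 12.6% | 21.8% | 48.6% |
| 40% | 4.3% | 10.5% | 19.8% | 44.8% |

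Check by the normal approximation, power ≈ Φ{[δ − 1.96·√(2p̄(1−p̄)/n)] / √([p(1−p) + (p+δ)(1−p−δ)]/n)}, where p̄ is the mean of the two rates. For p = 0.10 and δ = 0.05: (0.05 − 1.96·0.01763)/0.01758 = 0.88, giving 81%. For p = 0.40 and δ = 0.03: (0.03 − 1.96·0.02626)/0.02625 = −0.82, giving 21%. Both agree with the table. By the same approximation, the chance reaches 50% at an excess of 3.4 points (base 10%) to 5.2 points (base 40%).

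Both p and δ are assumptions. The only anchor in the documents is the investigator survey in section 5.3.2, where half reported proning in fewer than 40% of patients with P/F below 150. That is a survey answer, not an expected rate per arm.

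**4. What SAP 2.9 would then do.** With treatment received coded yes/no, the simple instrumental-variable estimate is (R_B − R_C)/(T_B − T_C), where R is the proportion with rescue and T the proportion receiving blockade in each arm. With no drug effect, R_B − R_C = −δ, so the estimate centres on −δ/(T_B − T_C) when the true value is zero. As T_B − T_C is at most 1, the bias is at least δ in size: 3 to 5 points or more for an excess of 3 to 5 points. The analysis is triggered by significance, so for a given p and δ the table also gives the chance that it is run.

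**The case against.** The strongest reply is that the trial compares two management strategies and that the outcome is named for use, not need. If one strategy brings more proning, the difference is a true intention-to-treat effect, and Fisher's test keeps its level for the hypothesis of equal use. This stands. A reader might infer that the test fails to hold its 5% error rate, or that the investigators would report a control excess as a benefit of cisatracurium. The documents support neither: no passage calls a rescue difference a drug effect. The nearest is SAP 2.9, and the objection does not answer that.

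Other points also stand.

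- Neither document defines an any-of composite. The A1 row could mean one test or one per procedure, so a single combined test is only one reading.
- Only the encouragement is one-sided. Access to proning is not.
- The size and even the direction of the net shift are unknown. Section 5.2.1 also encourages recruitment maneuvers, deeper sedation and diuresis, which are not counted and might replace proning.
- A reader might infer that dropping proning leaves a clean measure of need. It does not. The summary's advice is general and the 5.2.1 list is open-ended, so the other four procedures may also be affected. More proning in controls could also avert their later use.

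**Conclusion.** The concern holds as one of interpretation, and of the SAP 2.9 analysis, for one secondary outcome. Use of rescue procedures, as recorded, measures what the two strategies led clinicians to do. It cannot support a statement about need for rescue, or about safety or benefit of blockade, and the instrumental-variable estimate for it would rest on an assumption that the control-arm advice breaks.

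The range of about 20% to 80% against about 4% is illustrative. It rests on 704 per arm, no drug effect on need, base rates of 10% to 40% and an advice-driven excess of 3 to 5 points, and the documents supply neither the base rate nor the excess. It shows that a modest excess would often be significant in a trial of this size, not that one will occur. The primary outcome and the sample size are untouched.

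**What to change.** Amend the SAP, chiefly the Appendix A1 row:

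1. Report each rescue component by arm. Protocol section 6.3.2 already lists the five procedures separately.
2. Define the any-rescue outcome, and show it both with and without proning. Use the version without proning (nitric oxide, epoprostenol, high frequency ventilation, ECMO) when commenting on need for rescue. State that the control-arm advice is open-ended, so this reduces the problem but does not remove it.
3. Report proning as a co-intervention that was encouraged in the control arm, and label the contrast an effect of strategy.
4. In section 2.9, exclude this outcome, or state that the assumption that assignment acts only through treatment received is violated for it.

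The cost is wording. No new data are needed. The version without proning will have fewer events, and so slightly less power.

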### **Inclusion Criteria**

1. Age  $\geq$  18 years
2. Presence of all of the following conditions for  $\leq$  48 hours

- i. (I) PaO2/FiO2 < 150 with PEEP  $\geq$  8 cm H2O.a,b,c

#### **OR, IF ABG NOT AVAILABLE**

SpO2/FiO2 ratio that is equivalent to a PaO2/FiO2 < 150 with PEEP  $\geq$  8 cm H2O (Appendix A1), and a confirmatory SpO2/FiO2 ratio between 1-6 hours after the initial SpO2/FiO2 ratio determination.c,d

- ii. Bilateral opacities not fully explained by effusions, lobar/lung collapse, or nodules
- iii. Respiratory failure not fully explained by cardiac failure or fluid overload; need objective assessment (e.g., echocardiography) to exclude hydrostatic edema if no risk factor present (Appendix L)

a. If altitude >1000m, then PaO2/FiO2 < 150 x (PB/760).

b These inclusion criteria ensure a non-transient, established hypoxia that persists despite elevated PEEP and time. Initial, post-intubation, PEEP is typically < 8 cm H2O.

c The qualifying PaO2/FiO2 or the SpO2/FiO2 must be from intubated patients receiving at least 8 cm H2O PEEP.

d. When hypoxia is documented using pulse oximetry, a confirmatory SpO2/FiO2 ratio is required to further establish persistent hypoxia. Qualifying SpO2/FiO2 must use SpO2 values less than or equal to 96% Qualifying SpO2 must be measured at least 10 minutes after any change to FiO2.

The 48-hour enrollment time window begins when criteria i-iii are met. Criteria may be met at either the Network or referring hospital. The first qualifying SpO2/FiO2 (not the confirmatory SpO2/FiO2) is used determine this time window.

